9.2.1. Inclusion Criteria

Patients must meet all of the following inclusion criteria to be eligible for inclusion in the study:

- At least 1 observed prescription claim or medical claim for elranatamab or teclistamab in the
 dataset between August 14, 2023, and the most current date of data available. The index date will
 be the date of an individual's first claim. Patients who have received teclistamab before the
 August 14, 2023, date will require a period (i.e., 6 or 12 months) without a claim for teclistamab.
- 2. Age 18 or older on index date

- 3. Diagnosis of RRMM (defined as MM) any time prior to index date
- 4. At least 180 days of continuous closed-claims medical and pharmacy enrollment prior to index (inclusive) and 30 days post-index

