9.2. Setting

This study will evaluate adult patients with RRMM who initiate elranatamab or teclistamab. Patients will enter (i.e., index) on the first observed elranatamab or teclistamab claim between August 14, 2023 and March 2025. Limited eligibility criteria will be applied.

Study Period: Start of data (Jan 1, 2016) to the most current, available data.

MM diagnosis window: Start of data (Jan 1, 2016) to index date

Index date: First elranatamab or teclistamab claim after initial MM diagnosis

Observability: At least 180 days of continuous closed-claims medical and pharmacy enrollment prior to index (inclusive) and 30 days after the index date

Baseline period for MM-related treatments and MM-related comorbidities: MM diagnosis to one day prior to index date

Charlson Comorbidity Index and baseline HCRU assessment window: 180 days prior to index date to index date

Follow-up: Index date until death, the earliest of end of study period, or end of continuous enrollment (unless otherwise noted). Alternative censoring criteria will be applied for certain outcomes (such as OS, TTD, and TTNT/D).

Figure 1 reflects the time periods of interest in the study cohort. The data end date in Figure 1 will be updated at the time of the second, third, and final analyses, estimating data through June, September, and December 2025, respectively. All other dates shown in the figure will remain the same for the subsequent analyses.

[figure not shown]

Figure 1. Study Schematic for Patients Receiving Elranatamab or Teclistamab

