9.2.2. Exclusion Criteria

Patients meeting any of the following criteria will not be included in the study:

- 1. Enrollment in Medicare Advantage at any point during the study period
- 2. Age above 115 years old on the index date
- 3. Any patient that is receiving/has received both elranatamab and teclistamab during the study period

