9.3. Variables

Table 1 includes definitions and assessment periods for all study variables that will be used as eligibility criteria. The full code list can be found in ANNEX 2. ADDITIONAL INFORMATION.

Table 1. Variables Used to Determine Eligibility

Variable	Operational Definition	Assessment Period
Elranatamab	Prescription claim or medical claim with a National Drug Code (NDC), Healthcare Common Procedure Coding System (HCPCS), International Classification of Diseases, 10th Edition (ICD-10) code or generic name in the inpatient, non-inpatient or pharmacy setting for elranatamab	Index event
Teclistamab	Prescription claim or medical claim with an NDC, HCPCS, ICD-10 code or generic name in the inpatient, non-inpatient or pharmacy setting for teclistamab	Index event
Age	Age is greater than or equal to 18 years and is not missing	Index date
MM diagnosis	Medical claim in the inpatient or non-inpatient setting with an ICD-10 code for MM	All available data to index date
Observability	Closed-claims medical and pharmacy enrollment	180 days prior to index date to index date (inclusive) and 30 days post index
Medicare entitlement	Reason for Medicare entitlement	Index date

Table 2 includes definitions and assessment periods for all study variables that will be used as baseline and treatment characteristics. The full code list can be found in ANNEX 2. ADDITIONAL INFORMATION. If applicable, the frequency and percentage of patients with missing data for each variable will be described.

Table 2. Variables Used to Determine Baseline and Treatment Characteristics

Objective	Variable	Definition	Assessment Period(s)
1	Age	Age in years (continuous). Age will be calculated using the birth year variable from the beneficiary enrollment information.	Index date
1	Sex (assigned at birth)	Categorical sex	Index date
1	Race/Ethnicity	Beneficiary enhanced race/ethnicity designation based on first and last name algorithms and the Social Security Administration race code (modified using the Research Triangle Institute algorithm). Categorical race and ethnicity Caucasian African American Asian or Pacific Islander Hispanic or Latino Other Unknown	Index date
1	US Census Region	Categorical region, assessed as the most recent value from index date Northeast Midwest West South Unknown	Index date
1	State	State of residence	Index date

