Exploratory Obj 1	Other infectious hepatitis ²	Medical claim with an ICD-10 code in the inpatient, non-IP or pharmacy setting for infectious hepatitis (other than hepatitis B or C) (dichotomous)	Index date to end of follow-up, where follow-up will be based on last dose of elranatamab or teclistamab (e.g., 14 days after last recorded dose or 90 days after last recorded dose).
Exploratory Obj 1	Helicobacter pylori ²	Medical claim with an ICD-10 code in the inpatient, non-IP or pharmacy setting for helicobacter pylori (dichotomous)	Index date to end of follow-up, where follow-up will be based on last dose of elranatamab or teclistamab (e.g., 14 days after last recorded dose or 90 days after last recorded dose).

Exploratory Obj 1	Candida esophagitis ²	Medical claim with an ICD-10 code in the inpatient, non-IP or pharmacy setting for candida esophagitis (dichotomous)	Index date to end of follow-up, where follow-up will be based on last dose of elranatamab or teclistamab (e.g., 14 days after last recorded dose or 90 days after last recorded dose).				
Exploratory Obj 1	Urinary tract infection ²	Medical claim with an ICD-10 code in the inpatient, non-IP or pharmacy setting for a urinary tract infection (dichotomous)	Index date to end of follow-up, where follow-up will be based on last dose of elranatamab or teclistamab (e.g., 14 days after last recorded dose or 90 days after last recorded dose).				
Exploratory Obj 1	Time to infection onset	Time in days from index date to first infection for the following infections:	Index date until censor				
Effectiveness	Effectiveness						
Exploratory Obj 2	os	Time (in months) from index date until date of death (continuous)	Index date until censor				
Exploratory Obj 2	TTNT/D	Time (in months) from index date until the date of the next treatment (CAR-T, BsABs, bendamustine or belantamab) or death (continuous)	Index date until censor				

- 1. Variable will be measured as incident and prevalent. Incident cases have 30-day washout period applied
- 2. Variable will be measured as incident and prevalent. Incident cases have 60-day washout period applied
- 3. Variable will be measured as incident and prevalent. Incident cases have 14-day washout period applied

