9.7.7. Overall Survival and Time to Next Treatment

OS and TTNT/D will be assessed using unadjusted Kaplan-Meier methods. The median time to event in months will be reported along with the IQR. The 95% CIs for the median time to event will be calculated using log-log transformation. Results will be depicted graphically by Kaplan-Meier curves, and the percentage of patients who reached the outcome and censored patients will also be reported.

OS will be assessed as the time in months from index date to date of death. TTNT/D will be assessed as the time in months from index date until switch a new treatment or death. Patients will be censored at the earliest of death, next treatment (CAR-T, BsAbs, bendamustine or belantamab), the end of continuous closed-claim coverage, or the end of data. Patients without an event will be censored at the earliest of the end of continuous closed-claim coverage or end of data.

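### Cohort entry depends on post-index information: 30 days of enrolment with no written exception for death, and exclusion for any later Medicare Advantage enrolment

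*Protocol*

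**What the plan says.** Criterion 4 of Section 9.2.1 requires "At least 180 days of continuous closed-claims medical and pharmacy enrollment prior to index (inclusive) and 30 days post-index". The rule also stands in the Population paragraph of the abstract, in Section 9.2 ("Observability: At least 180 days of continuous closed-claims medical and pharmacy enrollment prior to index (inclusive) and 30 days after the index date") and in Table 1 of Section 9.3 ("180 days prior to index date to index date (inclusive) and 30 days post index"). None of the four places says what happens to a patient who dies inside the 30 days.

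The first exclusion in Section 9.2.2 is "Enrollment in Medicare Advantage at any point during the study period". Section 9.2 defines that period: "Study Period: Start of data (Jan 1, 2016) to the most current, available data". It therefore covers all time after index as well as before it.

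The outcome clocks nevertheless start at index. Section 9.2 gives "Follow-up: Index date until death, the earliest of end of study period, or end of continuous enrollment (unless otherwise noted", and Section 9.7.7 states "OS will be assessed as the time in months from index date to date of death". TTNT/D, TTD, the adverse-event windows and on-treatment resource use and costs also start at index (Sections 9.7.3 and 9.7.5 to 9.7.7). Sections 9.7.2 to 9.7.7 already censor patients when closed-claim coverage ends.

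**The concern.** Both rules use information from after time zero to decide who is in the cohort at time zero. If enrolment is taken to stop at death, the 30-day rule deletes every death in the first 30 days, while the survivors' first 30 days still count as time at risk. The Medicare Advantage rule deletes a patient who switches plan later, although that patient contributed valid claims up to the switch. Longer survivors have more time to switch, so this selection also depends on survival.

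The safety tables are the most exposed. Section 7 designates the study a PASS, Table 3 lists Grade 5 CRS and ICANS, and the step-up periods in Tables 4 and 5 (index to Day 8 for elranatamab, to Day 7 for teclistamab) lie wholly inside the 30 days. Section 9.4 allows a zero to be displayed, so a zero produced by the entry rule would look like an observed zero. Safety and survival are exploratory objectives, but primary Objectives 2 and 3 describe administration, resource use and costs in the same cohort. Section 9.9 discloses neither selection.

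**Working it through.** The protocol has no derived figure to reproduce: 133 (Section 9.5) is an observed count at August 2024 of patients with a claim. What follows only gauges the size of the effect. Mortality, median OS and switching rates are assumptions, because the protocol gives none.

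**Inputs.** Required window 30 days; 1 month = 30.4375 days (Section 9.7.5), so 30 days = 0.986 month; N = 133 for illustration only.

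**1. The 30-day rule, constant hazard.** With true median m months, the 30-day mortality is p = 1 − exp(−ln 2 × 0.986 / m). Conditioning on 30-day survival replaces S(t) by S(t)/(1 − p), and the exponential median becomes m + 0.986.

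| Assumed median OS (months) | Removed, p | Of 133 | Reported median (months) |
|---|---|---|---|
| 12 | 5.5% | 7.4 | 12.99 |
| 18 | 3.7% | 5.0 | 18.99 |
| 24 | 2.8% | 3.7 | 24.99 |

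For a true median of 12 months, 12-month OS would read 0.50/(1 − 0.055) = 0.529.

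**2. The 30-day rule, early mortality set freely.** The same division applies. A true 12-month OS of 60% reads 60.6%, 63.2% or 66.7% when 1%, 5% or 10% die within 30 days. The chance of deleting at least one of 133 is 1 − (1 − p)^133, which is already 74% at p = 1%.

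**3. Deleting post-index switchers.** Kaplan–Meier simulation with 1,000,000 patients per scenario: exponential OS, constant switching hazard, and uniform administrative censoring at 9 to 28.5 months (index from August 2023 to March 2025, data to December 2025).

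| True median (months) | Switching per year | Censor at switch | Delete switchers | Delete switchers and apply 30-day rule |
|---|---|---|---|---|
| 12 | 2% | 11.98 | 11.81 | 12.80 |
| 12 | 5% | 12.00 | 11.56 | 12.57 |
| 12 | 10% | 11.99 | 11.12 | 12.15 |
| 18 | 2% | 17.99 | 17.73 | 18.74 |
| 18 | 5% | 18.01 | 17.37 | 18.39 |
| 18 | 10% | 18.01 | 16.73 | 17.76 |

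Censoring at the switch recovers the true median. Deletion lowers it by about 0.2 to 0.9 month (true 12) or 0.3 to 1.3 months (true 18). With both rules the net error runs from about −0.2 month (17.76 against 18) to +0.8 month (12.80 against 12).

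**The case against.** The strongest reply is that the text does not say a death within 30 days fails criterion 4. Section 9.2 lists death separately from the end of enrolment, Section 9.7.5 censors at the end of coverage only patients without a discontinuation event or death, and Section 9.4 names mortality records as a data element. An unstated exception for death may be intended. This stands as a caution: deletion of early deaths is the literal reading, not an express statement. It does not remove the point, because the rule appears four times without the exception and Section 9.8 commits the analysts to follow the protocol strictly.

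Second, a reader might infer that the Medicare Advantage exclusion should be cut back to the 180-day baseline. The documents do not support that. Prior-treatment variables in Table 2 run from MM diagnosis, and pre-index resource use and costs in Section 9.7.3 run from the start of data. Care during an earlier Medicare Advantage spell that is absent from fee-for-service claims would count as no treatment and no cost. The pre-index look-back has a purpose; only the post-index reach is the defect.

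Third, the two biases oppose each other, and cells of 1 to 10 cannot be shown directly under Section 9.4, so a handful of early deaths might not be displayed anyway. Both statements are true. But any cancellation in OS would be chance, and neither suppression nor cancellation puts deleted early deaths back into the survival curves, the safety analysis or the costs.

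**Conclusion.** The point holds. As written, entry to the cohort depends on survival and plan choice after index, and the limitations section does not say so. On the literal reading, deaths in the first 30 days, including early fatal CRS or ICANS, are zero by construction. Alone, the 30-day rule removes 2.8% to 5.5% of initiators and lengthens median OS by about 1 month, given exponential survival with a median of 12 to 24 months. Alone, deleting switchers shortens median OS by about 0.2 to 1.3 months at 2% to 10% switching per year and a true median of 12 or 18 months.

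Two stronger readings go too far. One is that fatal toxicity cannot appear at all: deaths after day 30 remain, and the adverse-event windows run to 14 or 90 days after the last dose. The other is that OS will be overstated by a known amount, or the cohort reduced by a known number through the Medicare Advantage rule: the protocol gives no mortality or switching rate, and 133 is an August 2024 count, not the analysis cohort.

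**What to change.** - **Criterion 4**, in the abstract, Section 9.2, Section 9.2.1 and Table 1: require 180 days of enrolment before index, and either 30 days of enrolment after index or death within those 30 days. Dropping the post-index condition also works and is the cleaner choice, since short follow-up is then handled by censoring whether or not the patient dies.
- **Exclusion 1**, Section 9.2.2: limit it to Medicare Advantage enrolment on or before index, keeping the full pre-index look-back. State in the analysis sections that follow-up is censored at the first Medicare Advantage enrolment after index.
- **Attrition table**: report removals by reason, separating death, disenrolment and Medicare Advantage, subject to the CMS cell-size rule.
- **Section 9.9**: disclose any post-index condition that is kept.

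The cost is a few sentences of amendment and a rerun of cohort construction and the analyses on data already held. Patients are gained, which helps a study that describes its own expected sample as low. It should be done before the final analysis planned for 27 February 2026, because patients removed at cohort construction cannot be recovered by any later analysis.

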9.2.2. Exclusion Criteria

Patients meeting any of the following criteria will not be included in the study:

- 1. Enrollment in Medicare Advantage at any point during the study period
- 2. Age above 115 years old on the index date
- 3. Any patient that is receiving/has received both elranatamab and teclistamab during the study period

9.3. Variables

Table 1 includes definitions and assessment periods for all study variables that will be used as eligibility criteria. The full code list can be found in ANNEX 2. ADDITIONAL INFORMATION.

Table 1. Variables Used to Determine Eligibility

Variable	Operational Definition	Assessment Period
Elranatamab	Prescription claim or medical claim with a National Drug Code (NDC), Healthcare Common Procedure Coding System (HCPCS), International Classification of Diseases, 10th Edition (ICD-10) code or generic name in the inpatient, non-inpatient or pharmacy setting for elranatamab	Index event
Teclistamab	Prescription claim or medical claim with an NDC, HCPCS, ICD-10 code or generic name in the inpatient, non-inpatient or pharmacy setting for teclistamab	Index event
Age	Age is greater than or equal to 18 years and is not missing	Index date
MM diagnosis	Medical claim in the inpatient or non-inpatient setting with an ICD-10 code for MM	All available data to index date
Observability	Closed-claims medical and pharmacy enrollment	180 days prior to index date to index date (inclusive) and 30 days post index
Medicare entitlement	Reason for Medicare entitlement	Index date

Table 2 includes definitions and assessment periods for all study variables that will be used as baseline and treatment characteristics. The full code list can be found in ANNEX 2. ADDITIONAL INFORMATION. If applicable, the frequency and percentage of patients with missing data for each variable will be described.

Table 2. Variables Used to Determine Baseline and Treatment Characteristics

Objective	Variable	Definition	Assessment Period(s)
1	Age	Age in years (continuous). Age will be calculated using the birth year variable from the beneficiary enrollment information.	Index date
1	Sex (assigned at birth)	Categorical sex	Index date
1	Race/Ethnicity	Beneficiary enhanced race/ethnicity designation based on first and last name algorithms and the Social Security Administration race code (modified using the Research Triangle Institute algorithm). Categorical race and ethnicity Caucasian African American Asian or Pacific Islander Hispanic or Latino Other Unknown	Index date
1	US Census Region	Categorical region, assessed as the most recent value from index date Northeast Midwest West South Unknown	Index date
1	State	State of residence	Index date
1	Care setting	Categorical care setting for elranatamab or teclistamab administration Inpatient (IP) Non-IP Pharmacy	Index date, second treatment date, third treatment date, and overall

Objective	Variable	Definition	Assessment Period(s)
1	Time since MM diagnosis	Time (in months) from first MM diagnosis to index date (continuous)	MM diagnosis to index date
1	Income	Categorical household income	Index date
1	Education	Categorical level of highest education completed:	Index date
1	Marital Status	Categorical marital status:	Index date
1	Home Ownership	Categorical home ownership status: Renter Owner Unknown	Index date
1	Triple class exposed ¹⁷	 Medical claim in the IP, Non-IP or pharmacy setting with an NDC, HCPCS, Current Procedural Terminology (CPT), generic name, or ICD-10 procedure code for all the following therapies in the inpatient, non-IP, or pharmacy setting (dichotomous): ≥ 1 claim for PIs (see generic names below) ≥ 1 claim for IMiDs (see generic names below) ≥ 1 claim for CD38 mAbs (generic names: daratumumab, isatuximab) 	MM diagnosis to 1 day prior to index date
1	Penta-drug exposed ¹⁷	Medical claims with an NDC, HCPCS, CPT, generic name, or ICD-10 procedure codes in the inpatient, non-IP or pharmacy setting for all of the following therapies(dichotomous): • ≥ 2 distinct claims for PIs (see generic names below) • ≥ 2 distinct claims for IMiDs (see generic names below) • ≥ 1 claim for CD38 mAbs (generic names: daratumumab, isatuximab)	MM diagnosis to 1 day prior to index date

Objective	Variable	Definition	Assessment Period(s)
1	Hematopoietic Stem Cell Transplantation	Medical claim with an HCPCS, CPT, or ICD-10 code for hematopoietic stem cell transplantation in the inpatient, non-IP setting (dichotomous)	MM diagnosis to 1 day prior to index date
1	BCMA-directed therapy	Medical claim with an NDC, HCPCS CPT, generic name or ICD-10 procedure code in the inpatient, non-IP, or pharmacy setting for idecabtagene vicleucel, ciltacabtagene autoleucel, or belantamab (dichotomous)	MM diagnosis to 1 day prior to indexhe date Index date to the end
			of follow-up
1	CAR-T	Medical claim with an NDC, HCPCS, generic name or CPT code in the inpatient, non-IP, or pharmacy setting for idecabtagene vicleucel or ciltacabtagene autoleucel (dichotomous)	MM diagnosis to 1 day prior to index date
		autoreucer (dienotomous)	Index date to the end of follow-up
1	Talquetamab	Medical claim with an NDC, HCPCS, generic name or CPT code in the inpatient, non-IP, or pharmacy setting for talquetamab (dichotomous)	MM diagnosis to 1 day prior to index date
			Index date to the end of follow-up
1	PIs	Medical claim with an NDC, HCPCS, generic name or CPT code in the inpatient, non-IP, or pharmacy setting for bortezomib, carfilzomib, or ixazomib	MM diagnosis to 1 day prior to index date
		(dichotomous)	Index date to the end of follow-up
1	IMiDs	Medical claim with an NDC code or generic name in the non-IP or pharmacy setting for lenalidomide, thalidomide, or pomalidomide (dichotomous)	MM diagnosis to 1 day prior to index date
			Index date to the end of follow-up
1	Steroids	Medical claim with an NDC, HCPCS, generic name or CPT code in the inpatient, non-IP, or pharmacy setting for dexamethasone, methylprednisolone, prednisone, or prednisolone (dichotomous)	MM diagnosis to 1 day prior to index date
		prediffication, or prediffication (dieffotolificas)	Index date to the end of follow-up

Objective	Variable	Definition	Assessment Period(s)
1	mAbs	Medical claim with an NDC, HCPCS, generic name or CPT code in the inpatient, non-IP, or pharmacy setting for daratumumab, isatuximab, or elotuzumab (dichotomous)	MM diagnosis to 1 day prior to index date
			Index date to the end of follow-up
1	Chemotherapies	Medical claim with an NDC, HCPCS, generic name or CPT code in the inpatient, non-IP, or pharmacy setting for doxorubicin hydrochloride, melphalan, bendamustine, cyclophosphamide, etoposide, or	MM diagnosis to 1 day prior to index date
		cisplatin (dichotomous)	Index date to the end of follow-up
1	Small molecule inhibitors	Medical claim with an NDC, HCPCS, generic name or CPT code in the inpatient, non-IP, or pharmacy setting for venetoclax (dichotomous)	MM diagnosis to 1 day before index date
		setting for venerociax (dichotomous)	Index date to the end of follow-up
1	Nuclear export inhibitors	Medical claim with an NDC, HCPCS, generic name or CPT code in the inpatient, non-IP, or pharmacy setting for selinexor (dichotomous)	MM diagnosis to 1 day before index date
		coming for community (controlled as)	Index date to the end of follow-up
1	Antivirals	Medical claim with an NDC, HCPCS, generic name or CPT code in the inpatient, non-IP, or pharmacy setting for antiviral medications (dichotomous)	14 days prior to index date to 1 day prior to index date
1	Antibiotics	Medical claim with an NDC, HCPCS, generic name or CPT code in the inpatient, non-IP, or pharmacy setting for antibiotic medications (dichotomous)	14 days prior to index date to 1 day prior to index date
1	Antifungal Medication	Medical claim with an NDC, HCPCS, generic name or CPT code in the inpatient, non-IP, or pharmacy setting for antifungal medications (dichotomous)	14 days prior to index date to 1 day prior to index date
1	Intravenous immunoglobulin	Medical claim with an NDC, HCPCS, generic name, CPT, or ICD-10 procedure code in the inpatient, non-IP, or pharmacy setting for intravenous immunoglobulin administration (dichotomous)	MM diagnosis to 1 day prior to index date

Objective	Variable	Definition	Assessment Period(s)
1	Other hematological malignancies	Medical claim with an ICD-10 code in the inpatient or non-IP setting for hematological malignancies other than MM (dichotomous)	MM diagnosis to 1 day prior to index date
1	Any non- hematological malignancy	Medical claim with an ICD-10 code in the inpatient or non-IP setting for non-hematological malignancies (dichotomous)	MM diagnosis to 1 day prior to index date
1	Plasma cell leukemia	Medical claim with an ICD-10 code in the inpatient or non-IP setting for plasma cell leukemia (dichotomous)	MM diagnosis to 1 day prior to index date
1	Bone lesions	Medical claim with an ICD-10 code in the inpatient or non-IP setting for bone lesions (dichotomous)	MM diagnosis to 1 day prior to index date
1	Peripheral neuropathy	Medical claim with an ICD-10 code in the inpatient or non-IP setting for peripheral neuropathy (dichotomous)	MM diagnosis to 1 day prior to index date
1	Any infection	Medical claim with an ICD-10 code in the inpatient or non-IP setting for any infection of the following types (dichotomous): COVID-19 Adenoviral pneumonia Cytomegaloviral pneumonitis COVID-19 pneumonia Other Pneumonia Upper respiratory tract infection Sepsis Cytomegaloviral infection Pneumocystis jiroveci pneumonia (PJP) Hepatitis C Hepatitis B Other infectious hepatitis Helicobacter pylori Candida esophagitis Urinary tract infection Sinusitis Bronchitis	MM diagnosis to 1 day prior to index date
1	Use of intravenous anti-infective	Medical claim with an NDC code generic name, CPT, or HCPCS code in the inpatient, non-IP, or pharmacy setting for anti-infective where the route	MM diagnosis to 1 day prior to index date

Objective	Variable	Definition	Assessment Period(s)
		of administration is intravenous for an intravenous anti-infective (dichotomous)	
1	Neutropenia	Medical claim with an ICD-10 code in the inpatient or non-IP setting for neutropenia (dichotomous)	MM diagnosis to 1 day prior to index date
1	Hypercalcemia	Medical claim with an ICD-10 code in the inpatient or non-IP setting for hypercalcemia (dichotomous)	MM diagnosis to 1 day prior to index date
1	Hepatotoxicity	Medical claim with an ICD-10 code in the inpatient or non-IP setting for hepatotoxicity (dichotomous)	MM diagnosis to 1 day prior to index date
1	Renal failure	Medical claim with an ICD-10 code in the inpatient or non-IP setting for renal failure (dichotomous)	MM diagnosis to 1 day prior to index date
1	Amyloidosis	Medical claim with an ICD-10 code in the inpatient or non-IP setting for amyloidosis (dichotomous)	MM diagnosis to 1 day prior to index date
1	Hypertension	Medical claim with an ICD-10 code in the inpatient or non-IP setting for hypertension (dichotomous)	MM diagnosis to 1 day prior to index date
1	Extramedullary disease	Medical claim with an ICD-10 code in the inpatient or non-IP setting for extramedullary disease (dichotomous)	MM diagnosis to 1 day prior to index date
1	Charlson Comorbidity Index (CCI) score	CCI ¹⁸ (continuous and categorical): • 0 (no comorbidities) • 1 to 2 (mild) • 3 to 4 (moderate) • ≥ 5 (severe)	180 days prior to index date to index
1	Myocardial infarction	Medical claim with an ICD-10 code in the inpatient or non-IP setting for myocardial infarction (dichotomous)	180 days prior to index date to index
1	Congestive heart failure	Medical claim with an ICD-10 code in the inpatient or non-IP setting for congestive heart failure (dichotomous)	180 days prior to index date to index date

Objective	Variable	Definition	Assessment Period(s)
1	Peripheral vascular disease	Medical claim with an ICD-10 code in the inpatient or non-IP setting for peripheral vascular disease (dichotomous)	180 days prior to index date to index
1	Cerebrovascular disease	Medical claim with an ICD-10 code in the inpatient or non-IP setting for cerebrovascular disease (dichotomous)	180 days prior to index date to index
1	Dementia	Medical claim with an ICD-10 code in the inpatient or non-IP setting for dementia (dichotomous)	180 days prior to index date to index
1	Chronic pulmonary disease	Medical claim with an ICD-10 code in the inpatient or non-IP setting for chronic pulmonary disease (dichotomous)	180 days prior to index date to index
1	Rheumatic disease	Medical claim with an ICD-10 code in the inpatient or non-IP setting for rheumatic disease (dichotomous)	180 days prior to index date to index
1	Peptic ulcer disease	Medical claim with an ICD-10 code in the inpatient or non-IP setting for peptic ulcer disease (dichotomous)	180 days prior to index date to index
1	Liver disease	Medical claim with an ICD-10 code in the inpatient or non-IP setting for liver disease (dichotomous)	180 days prior to index date to index
1	Diabetes	Medical claim with an ICD-10 code in the inpatient or non-IP setting for diabetes (dichotomous)	180 days prior to index date to index
1	Renal disease	Medical claim with an ICD-10 code in the inpatient or non-IP setting for renal disease (dichotomous)	180 days prior to index date to index date
1	Hemiplegia or paraplegia	Medical claim with an ICD-10 code in the inpatient or non-IP setting for hemiplegia or paraplegia (dichotomous)	180 days prior to index date
1	Human immunodeficienc y virus	Medical claim with an ICD-10 code in the inpatient or non-IP setting for human immunodeficiency virus (dichotomous)	180 days prior to index date to index date

Objective	Variable	Definition	Assessment Period(s)
1	Metastatic solid tumor	Medical claim with an ICD-10 code in the inpatient or non-IP setting for metastatic solid tumor (dichotomous)	180 days prior to index date to index date

Table 3 includes definitions and assessment periods for all study variables being used as outcomes. The full code list can be found in ANNEX 2. ADDITIONAL INFORMATION. If applicable, the frequency and percentage of patients with missing data for each variable will be described.

Table 3. Key Variables of Interest

Objective	Variable	Definition	Assessment Period(s)
Treatment ex	posure		
2	Use of supportive MM medications	Medical or pharmacy claim with evidence of an NDC, HCPCS, generic name or CPT code for the following medications (dichotomous):	Index date to the end of follow-up Index date Step-Up Dosing Period Maintenance Periods
2	Reported vial size	Reported vial size in the following categories (categorical): • Unknown vial – inpatient dose • 44mg/1.1mL • 76mg/1.9mL • Missing dose/unknown dose For the cohort of teclistamab patients the reported vial size (categorical): • Unknown vial – inpatient dose • 30mg/3mL • 153mg/7mL • Missing dose/unknown dose	Index date to the end of follow-up Index date Step-Up Dosing Period Maintenance Periods
2	Average time between elranatamab or teclistamab claims	Sum of the days between claims for the index drug (continuous) divided by the total number of administrations -1	Index date to the end of follow-up Step-Up Dosing Period

	1	T	T
			Maintenance Periods
2	Frequency of elranatamab or	Total number of inpatient, non-IP, and pharmacy claims of the index drug during the	Index date to the end of follow-up
	teclistamab claims	time period based on vial size (continuous)	Step-Up Dosing Period
			Maintenance Periods
2	Relative Administration Intensity (RAI)	The ratio of the actual administrations received divided by the expected number of administrations according to the US label	Index date to the end of follow-up
		(continuous)	Step-Up Dosing Period
			Maintenance Periods
2	Time to Discontinuation (TTD)	Time in months from first administration until last administration prior to treatment discontinuation (continuous). Treatment discontinuation is defined as an 8-week gap in elranatamab or teclistamab therapy, next treatment after index treatment (CAR-T, BsABs, bendamustine or belantamab), or death.	Index date to the end of follow-up
2	Reason for Discontinuation	Reason for treatment discontinuation used to estimate time to discontinuation, either an 8-week gap in elranatamab or teclistamab therapy, next treatment after index treatment (CAR-T, BsABs, bendamustine or belantamab), or death.	Index date to the end of follow-up
Health care	resource utilization an	d costs	
3	All-cause IP visits	Medical claim for IP (non-emergency department [ED]) visit (dichotomous)	Start of data to 1 day before index date, index date until last recorded dose, and time from discontinuation through time of censoring
		Number of IP (non-ED) visits (continuous)	
3	All-cause OP visits	Medical claim for non-IP/non-ED visit (dichotomous)	Start of data to 1 day before index date, index date until last recorded dose, and time from
		Number of non-IP/non-ED visits (continuous)	discontinuation through time of censoring

3	All-cause ED visits	Medical claim for ED visit (dichotomous) Number of ED visits (continuous)	Start of data to 1 day before index date, index date until last recorded dose, and time from discontinuation through time of censoring
3	All-cause pharmacy claims	Pharmacy claim (dichotomous) Number of pharmacy claims (continuous)	Start of data to 1 day before index date, index date until last recorded dose, and time from discontinuation through time of censoring
3	Total duration of all-cause IP stays	The total time in days of IP stays among patients who have at least 1 IP stay (continuous).	Start of data to 1 day before index date, index date until last recorded dose, and time from discontinuation through time of censoring
3	Total all-cause HCRU	IP, OP, ED, or pharmacy claims (dichotomous) Number of IP, OP, ED, or pharmacy claims	Start of data to 1 day before index date, index date until last recorded dose, and time from discontinuation through
3	MM-related IP visits	(continuous) Medical claim for IP (non-ED) visit with an MM ICD-10 code or treatment for MM (dichotomous) Number of IP (non-ED) visits with an MM	Start of data to 1 day before index date, index date until last recorded dose, and time from discontinuation through time of censoring
3	MM-related OP visits	ICD-10 code or treatment for MM (continuous) Medical claim for non-IP/non-ED visit with an MM ICD-10 code or treatment for MM (dichotomous)	Start of data to 1 day before index date, index date until last recorded dose, and time from
		Non-IP/non-ED visits with an MM ICD-10 code or treatment for MM (continuous)	discontinuation through time of censoring

	1		
3	MM-related pharmacy claims	Pharmacy claim with a treatment for MM (dichotomous)	Start of data to 1 day before index date, index date until last recorded dose, and time from
		Number of pharmacy claims with a treatment for MM (continuous)	discontinuation through time of censoring
3	Total duration of MM-related IP stays	The total time in days of IP stays with an MM ICD-10 code or treatment for MM, among patients who have at least 1 IP stay (continuous)	Start of data to 1 day before index date, index date until last recorded dose, and time from discontinuation through time of censoring
3	Total MM-related HCRU	IP, OP, ED, or pharmacy claims with an MM ICD-10 code or treatment for MM (dichotomous)	Start of data to 1 day before index date, index date until last recorded dose, and time from discontinuation through
		IP, OP, ED, or pharmacy claims with an MM ICD-10 code or treatment for MM (continuous)	time of censoring
3	Cost of all-cause IP visits	Cost of IP (non-ED) visits (continuous)	Start of data to 1 day before index date, index date until last recorded dose, and time from discontinuation through time of censoring
